15.7. Biogen Responsibilities

Biogen's responsibilities include the following:

- Before study site activation and subject enrollment, the Clinical Monitor or designee is responsible for reviewing with study site staff the definitions of AE and SAE, as well as the instructions for monitoring, recording, and reporting AEs and SAEs.
- Biogen is to notify all appropriate regulatory authorities, central ethics committees, and Investigators of SAEs, as required by local law, within required time frames.

CONFIDENTIAL

The information contained herein may not be used, disclosed, or published without the written consent of
Biogen MA Inc.

16. STATISTICAL METHODS AND DETERMINATION OF SAMPLE SIZE

16.1. Description of Objectives

See Section 6.1, Objectives.

16.2. Description of Endpoints

See Section 6.2, Endpoints.

16.3. Demography and Baseline Disease Characteristics

Demographic data collected at baseline will be summarized (i.e., age, gender, ethnicity, and weight). Medical history and baseline characteristic data (e.g., EDSS, number of relapses in the previous study, MRI endpoints) will also be summarized.

16.4. Safety and Efficacy

16.4.1. Analysis Population

Study 205MS303 Safety Population

The safety population will include all subjects who received at least 1 dose of DAC HYP in Study 205MS303. All safety analyses will be completed on the safety population.

Study 205MS303 Intent-to-Treat Population

The intent-to-treat (ITT) population will include all subjects who received at least 1 dose of DAC HYP in Study 205MS303. This population will be utilized for the efficacy analyses.

Study 205MS301 and Study 205MS303 Intent-to-Treat population

This population will include all subjects randomized to DAC HYP or Avonex in Study 205MS301 and received at least one dose of DAC HYP in Study 205MS303.

16.4.2. General Methods of Analysis

Summary statistics will be presented. For continuous endpoints, summary statistics will generally include the number of subjects with data, mean, standard deviation, median, and range. Categorical endpoints will include the number of subjects with data and the percentage in each category.

Analyses will generally be descriptive in nature and will focus on data collected during Study 205MS303 only. However, for relevant efficacy analyses, the data may be summarized by previous treatment group (Avonex or DAC HYP). Also, statistical comparisons may be made between efficacy in Study 205MS301 and efficacy in Study 205MS303 among subjects previously randomized to Avonex in Study 205MS301.

All statistical tests will be 2-sided with an overall Type I error of 5%. Adjustments for multiple comparisons will not be considered.

CONFIDENTIAL

The information contained herein may not be used, disclosed, or published without the written consent of Biogen MA Inc.

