16.4.5. Efficacy Endpoints Analyses

Annualized Relapse Rate

Relapses will be summarized over the follow-up period in Study 205MS303. For subjects in Study 205MS301 and Study 205MS303 ITT population, relapses may be summarized over the combined study period (Studies 205MS301 and 205MS303).

A negative binomial regression model will be used to estimate the adjusted ARR.

Proportion of Subjects with a Relapse

The proportion of subjects relapsed will be estimated using a Kaplan-Meier curve.

Disability Progression

Sustained disability progression is defined as at least a 1.0 point increase on the EDSS from baseline EDSS ≥ 1.0 that is sustained for 24 weeks, or at least a 1.5 point increase on the EDSS from baseline EDSS < 1.0 that is sustained for 24 weeks. The proportion of subjects with progression will be summarized using a Kaplan-Meier curve. In addition, summary statistics for EDSS and for the change from baseline in EDSS will be presented by visit, and for subjects who participated in Study 205MS301, by previous treatment group.

MSFC

Changes in the MSFC z-score will be summarized by study visit, and for subjects who participated in Study 205MS301, by previous treatment group. For subjects in Study 205MS301 and Study 205MS303 ITT population, MSFC z-score may be summarized over the combined study period (Studies 205MS301 and 205MS303). Details on the calculations of the z-score for each component will be described in the statistical analysis plan.

SDMT

Changes in the SDMT scores will be summarized by study visit and by previous treatment group in Study 205MS301. Change in the SDMT scores over the combined study period (Studies 205MS301 and 205MS303) will be calculated using the Study 205MS301 baseline visit

CONFIDENTIAL

The information contained herein may not be used, disclosed, or published without the written consent of Biogen MA Inc.

as baseline. Change in the SDMT score over the Study 205MS303 study period will be calculated using the last SDMT measurement in Study 205MS301 as baseline.

PASAT 3

Changes in the PASAT 3 scores will be summarized by study visit and by previous treatment group in Study 205MS301. Change in the PASAT 3 scores over the combined study period (Studies 205MS301 and 205MS303) will be calculated using the Study 205MS301 baseline visit as baseline. Change in the PASAT 3 score over the Study 205MS303 study period will be calculated using the Week 0/baseline visit as baseline.

MRI Endpoints

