16.5. Interim Analyses

No formal interim analyses are planned for this study. However, analyses may be performed prior to the end of the study at the discretion of the Sponsor.

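### Section 16.4.2 calls its 5% Type I error overall but excludes any multiplicity adjustment, so the 5% is true only per test

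*Protocol*

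**What the plan says.** Section 16.4.2 (General Methods of Analysis) sets the error rate for the whole plan: "All statistical tests will be 2-sided with an overall Type I error of 5%. Adjustments for multiple comparisons will not be considered". The same section describes the general character of the work: "Analyses will generally be descriptive in nature and will focus on data collected during Study 205MS303 only". It then opens one route to formal testing: "Also, statistical comparisons may be made between efficacy in Study 205MS301 and efficacy in Study 205MS303 among subjects previously randomized to Avonex". That sentence names a subgroup but neither an endpoint nor a number of comparisons.

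Section 16.4.5 goes through the efficacy endpoints, and most of its wording is about estimation. For relapse rate: "A negative binomial regression model will be used to estimate the adjusted ARR". For relapse as a proportion: "The proportion of subjects relapsed will be estimated using a Kaplan-Meier curve". Progression, EDSS, MSFC, SDMT, PASAT 3 and quality of life are summarised. New or newly enlarging T2 lesions are analysed with a negative binomial model and lesion volume change with an analysis of covariance, but no contrast is named for either.

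Section 16.5 says that no formal interim analyses are planned, then adds that "analyses may be performed prior to the end of the study at the discretion of the Sponsor". Section 16.4.3 summarises adverse-event incidence, the primary endpoint, without a test. Section 16.6 gives no formal sample size calculation.

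The two sentences on Type I error also stand in Section 16.4.2 of both earlier protocol versions in the file.

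**The concern.** An overall Type I error, applied to all statistical tests, is the probability of at least one false rejection across the set. Testing each comparison at 5% with no adjustment gives a 5% rate per comparison, which is a different and weaker property. The plan claims the first and specifies the second.

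What is at stake is how any p-values from the 205MS301-versus-205MS303 comparisons may be described. These would be before-and-after contrasts in an open-label, single-arm extension, restricted to subjects who went on to take at least one dose of DAC HYP in 205MS303. An isolated result below 0.05 in that setting should not be able to cite a protocol sentence saying that the overall error was held at 5%.

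**Working it through.** **Inputs**

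- Alpha: 0.05, two-sided, described as overall (Section 16.4.2).
- Adjustment: none (Section 16.4.2).
- Number of tests, *k*: not stated. The comparisons are optional and no endpoint is fixed, so *k* is an assumption here. I use 2 and 4.
- Correlation between test statistics, *rho*: not stated, also an assumption. I use values from 0 to 0.9.

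**Reproducing the plan's figure.** For *k* independent tests, each at 5%, the chance of at least one false positive is 1 − 0.95^k.

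- *k* = 1: 1 − 0.95 = 0.050. The stated 5% is recovered.
- *k* = 2: 1 − 0.95² = 1 − 0.9025 = 0.0975.
- *k* = 4: 1 − 0.95⁴ = 1 − 0.8145 = 0.1855.

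The stated figure is therefore recovered only for a single test, that is, when it is read as a per-test level.

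**Allowing for correlation.** Efficacy endpoints measured in the same subjects are related; relapse rate and proportion relapsed even come from the same events. I took *k* equally correlated standard normal statistics, rejected each when its absolute value exceeded the two-sided 5% critical value, and simulated 400,000 sets per case. The simulation standard error is at most √(0.1734 × 0.8266 / 400,000) ≈ 0.0006.

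| Correlation | Two tests | Four tests |
|---|---|---|
| 0 (formula) | 9.75% | 18.55% |
| 0.3 | 9.43% | 17.34% |
| 0.5 | 9.15% | 15.59% |
| 0.8 | 7.81% | 11.34% |
| 0.9 | 7.03% | 9.45% |

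Every entry exceeds 5%. The rate returns to 5% only if the statistics are perfectly correlated or only one test is done.

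**What keeping the claim would require.** To hold an overall 5%, Bonferroni would test at 0.05/2 = 0.025 for two tests, giving 1 − 0.975² = 0.0494 under independence, or at 0.05/4 = 0.0125 for four, giving 1 − 0.9875⁴ = 0.0491. The protocol rules this route out, so the wording has to change instead.

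**The case against.** The strongest reply is that the paragraph discloses its own limits. It calls the analyses generally descriptive and says plainly that "Adjustments for multiple comparisons will not be considered". Read as a whole, the natural meaning is a conventional two-sided 5% level per test, loosely worded. Much of this stands. A careful reader is unlikely to be misled for long, and leaving tests unadjusted is acceptable in a study of this kind. It does not rescue the word *overall*: if a per-test level was meant, the word is wrong and should go.

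A second reply is that the choice of contrasts belongs in the statistical analysis plan, which is not shown. That is right as to which tests are run, and if exactly one were run the sentence would be true. It would not help with two or more, because the protocol itself excludes the adjustment that would make the claim hold.

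Stronger readings are tempting. A reader might infer that every endpoint in Section 16.4.5 is tested at 5%, so that 10 or 20 tests would give 1 − 0.95^10 = 40% or 1 − 0.95^20 = 64%. The documents do not support that: most of those endpoints are estimated or summarised, the between-study comparisons are optional, and no count of 10 or 20 appears anywhere. A reader might also infer that early analyses add further inflation. Section 16.5 says that no formal interim analyses are planned, refers to analyses rather than tests, and attaches no efficacy decision to them, so no such inflation can be derived.

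**Conclusion.** The statement is wrong as written. An overall 5% error rate cannot hold for two or more unadjusted 5% tests unless they are perfectly correlated, and Section 16.4.2 permits comparisons on more than one endpoint. The excess is about 8 to 10% against 5% for two tests and about 11 to 19% for four. Those ranges rest on assumed numbers of tests and on equal correlations from 0.8 down to zero; stronger correlation would lower them, and a single test would remove the problem.

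The severity is low. The primary safety endpoint is summarised without a test, no sample size depends on alpha, and the consequence is confined to how secondary efficacy p-values may be described. This is not a finding that the trial needs multiplicity control.

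**What to change.** In Section 16.4.2, delete the word *overall* and reword along these lines: any statistical tests are two-sided at a nominal 5% level per comparison, with no adjustment for multiple comparisons and no control of the overall Type I error.

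The cost is one sentence. No analysis, data collection or sample size changes. The only thing given up is a claim of error control that the plan does not deliver.

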16.4.3. Primary Endpoints Analysis

Clinical Adverse Events

AEs will be coded using the Medical Dictionary for Regulatory Activities. All treatment-emergent events will be included in the evaluation of safety. Treatment emergent includes any event that either occurs or worsens in severity after the onset of study treatment. Overall incidence of treatment-emergent events will be summarized; in addition, summaries by severity and by relationship to study treatment will be provided. The summary tables will include incidence estimates for the overall system organ class as well as for preferred terms within each system organ class. In order to assess whether the incidence of events changes over time, the incidence of key events may also be summarized by time period (e.g., 6-month time intervals).

16.4.4. Other Safety Endpoint Analyses

Unless otherwise specified, the baseline measurement for safety assessments such as laboratory values and vital signs was the measurement acquired on the day of the first receipt of DAC HYP. The first receipt of dosing of DAC HYP could be either Study 205MS303 (for subjects who received Avonex in Study 205MS301) or the parent studies (i.e., Study 205MS301, Study 205MS203, or Study 205MS302) for all other subjects.

Laboratory Data

Changes in laboratory values will be summarized using shift tables. Shift tables will include hematology, LFTs, kidney function tests, electrolytes, and other blood chemistry tests. Shifts will be presented from baseline of DAC HYP treatment (the last measurement acquired before or on the day of the first receipt of DAC HYP, e.g., Study 205MS303 baseline for subjects randomized to Avonex in Study 205MS301 and Study 205MS301 baseline for subjects randomized to DAC HYP 150 mg in Study 205MS301). Summaries of worst post-baseline laboratory values by clinically relevant categories may also be presented for selected parameters of interest by treatment group. For example, for LFT (alkaline phosphatase, ALT, AST, GGT, and total bilirubin), categories may be defined based on cutoff values relative to the ULN.

Vital Signs

Vital signs collected will be examined to determine the incidence of clinically relevant abnormalities. These abnormalities are described in [Table 8](#). For the purpose of the shifts from baseline, the baseline evaluation at the start of DAC HYP treatment will be used.

For each vital sign, the number of subjects evaluated and the number and percentage of subjects with the defined abnormality at any time post dosing will be presented by treatment group.

CONFIDENTIAL

The information contained herein may not be used, disclosed, or published without the written consent of Biogen MA Inc.

Table 8: Criteria to Determine Clinically Relevant Abnormalities in Vital Signs

Vital Sign	Criteria for Abnormalities
Temperature	>38°C or an increase from baseline of $\geq 1^\circ\text{C}$
Pulse	>120 beats per minute (bpm) or an increase from baseline of 20 bpm <50 bpm or a decrease from baseline of >20 bpm
Systolic Blood Pressure	>180 mmHg or an increase from baseline of >40 mmHg <90 mmHg or a decrease from baseline of >30 mmHg
Diastolic Blood Pressure	>105 mmHg or an increase from baseline of >30 mmHg <50 mmHg or a decrease from baseline of >20 mmHg

Physical Examination

The physical examination findings will be summarized.

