14. SCHEDULE OF EVENTS

14.1. Overview

A written, signed Informed Consent Form (ICF) and all authorizations required by local law (e.g., Protected Health Information [PHI] in North America) must be obtained prior to performing any tests or assessments under this protocol.

For subjects entering from Study 205MS301, tests/assessments performed at the subject's last visit in Study 205MS301 and within 28 days of the subject's first dose of DAC HYP (Week 0) in Study 205MS303 may be used as baseline data for Study 205MS303; if final Study 205MS301 tests/assessments are not performed within the 28-day window, they must be repeated upon entry into Study 205MS303 and before the first dose of DAC HYP is administered.

Week 144 Visit of Study 205MS303 will be the Entry Visit for subjects enrolled from Study 205MS203 or Study 205MS302. Any test/assessment done at the subject's last visit in parent studies and within 28 days of the subject's first dose in Study 205MS303 will be used as the baseline and does not need to be repeated at entry into Study 205MS303; test/assessments performed >28 days before the Entry Visit must be repeated at the Entry Visit. Central LFT testing is *mandatory* at Entry Visit.

Clinic visits will occur once every 4 weeks for the first 12 weeks, then every 12 weeks thereafter.

On a dosing day, all tests and assessments must be performed prior to DAC HYP administration. When DAC HYP administration and MRI evaluation are required at the same visit, the MRI scan should be performed prior to DAC HYP administration (Note: MRI scan can be performed up to 4 days prior to the visit).

Before a monthly dose of DAC HYP is given, LFT results (ALT/SGPT, AST/SGOT, alkaline phosphatase, total bilirubin, and GGT only) from prior testing performed within 28(+4) days must be reviewed by the *Study Neurologist* or their backup, and must be within the protocol-required limits.

After Week 12, subjects will have the option of administering DAC HYP at home following Investigator review of monthly pre-dose LFT results. Subjects who are not able to administer their own dose or prefer not to administer their own dose of DAC HYP will be given the option to choose another individual (caregiver) to administer their treatment at home or to have their treatment administered by staff at the study site.

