Study 205MS201 (SELECT) was a double-blind, placebo-controlled study to evaluate the safety and efficacy of DAC HYP in subjects with RRMS that randomized 621 subjects in a 1:1:1 ratio to receive placebo, 150 mg DAC HYP, or 300 mg DAC HYP SC every 4 weeks over a 52-week treatment period. Among subjects randomized to DAC HYP (150 mg, 300 mg) versus placebo, there was a significantly lower annualized relapse rate (ARR; 0.21, 0.23 versus 0.46; $p < 0.001$), a higher proportion of relapse-free subjects (81%, 80% versus 64%; $p < 0.001$), and a trend towards improvement in the MSIS-29 physical score ($p = 0.128$ for DAC HYP 300 mg versus placebo; $p < 0.001$ for DAC HYP 150 mg versus placebo). There were significant reductions in the mean number of new or newly enlarging T2 lesions at 1 year (2.4, 1.7 versus 8.1) and in the mean number of new Gd+ lesions between Weeks 8 and 24 in a monthly MRI substudy ($n = 307$) (1.5, 1.0 versus 4.8) in the DAC HYP 150 mg and 300 mg groups versus placebo ($p <$

CONFIDENTIAL

The information contained herein may not be used, disclosed, or published without the written consent of Biogen Idec Inc.

0.001 for all comparisons). The risk of 3-month sustained disability progression at 1 year, a tertiary study endpoint, was reduced by 57% ($p = 0.021$) in the DAC HYP 150 mg group and by 43% ($p = 0.091$) in the DAC HYP 300 mg group.

Analysis of safety data from Study 205MS201 showed that, overall, DAC HYP was well tolerated in this patient population. The most frequently reported ($\geq 10\%$) AEs for subjects treated with DAC HYP, excluding MS relapse, were nasopharyngitis (14%), and headache and upper respiratory tract infection (10% each). In Study 205MS201, serious adverse events (SAEs) including MS relapses occurred in 26% of placebo-treated subjects and in 16% of subjects treated with DAC HYP. Excluding MS relapses, SAEs occurred in 6% of the placebo group, in 7% of the DAC HYP 150 mg group, and in 9% of the DAC HYP 300 mg group. One DAC HYP-treated subject died due to ischemic colitis following a complicated course of events. Adverse events observed more frequently in DAC HYP-treated patients included an increase in serious infections (2%), serious cutaneous events (1%), and elevations in liver function tests (ALT/AST) $>5 \times$ ULN (4%).

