Upon completion of the 12-month treatment period in Study 205MS201, subjects were eligible to complete up to an additional 12 months of treatment with DAC HYP in a double-blind extension study (Study 205MS202 [SELECTION]), which was completed in 2012. Study 205MS202 also assessed the effects of DAC HYP washout in some subjects who were actively treated in Study 205MS201. Subjects completing Study 205MS202 continued long-term therapy with open-label DAC HYP in extension Study 205MS203 (SELECTED), which evaluated long-term safety and efficacy of DAC HYP monotherapy for up to an additional 144 weeks.

Study 205MS301

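### Section 16.4.4 sets the safety baseline at first DAC HYP exposure, but its list of studies includes 205MS203 and omits 205MS201 and 205MS202, where 205MS203 subjects were first exposed

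*Protocol*

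**What the plan says.** Protocol Section 16.4.4 (Other Safety Endpoint Analyses) opens with a default, subject to exceptions stated elsewhere: the baseline for safety assessments "was the measurement acquired on the day of the first receipt of DAC HYP". It then says where that day can fall. For subjects given Avonex in 205MS301 it is in 205MS303. Otherwise it is in "the parent studies (i.e., Study 205MS301, Study 205MS203, or Study 205MS302) for all other subjects".

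Two measures have their own wording in the same section. Laboratory shift tables use "the last measurement acquired before or on the day of the first receipt of DAC HYP", with examples drawn only from the two arms of 205MS301. For vital-sign shifts, "the baseline evaluation at the start of DAC HYP treatment will be used".

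Section 5.1 gives the history of the 205MS203 subjects. Study 205MS201 "randomized 621 subjects in a 1:1:1 ratio to receive placebo, 150 mg DAC HYP, or 300 mg DAC HYP SC every 4 weeks" over 52 weeks. Those who completed it could then receive "up to an additional 12 months of treatment with DAC HYP in a double-blind extension study", Study 205MS202. After that, "Subjects completing Study 205MS202 continued long-term therapy with open-label DAC HYP in extension Study 205MS203".

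**The concern.** The criterion and the list point to different studies for one group of subjects. A person who follows the criterion takes the baseline of a 205MS203-route subject from 205MS201 or 205MS202. A person who follows the list takes it from 205MS203 entry. The resulting shift tables differ.

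Under the list, one column headed as baseline would mix two things. 205MS301 entrants would contribute a value from before any DAC HYP. 205MS203 entrants would contribute a value from after earlier exposure. A transaminase or blood-count abnormality that arose in 205MS201 or 205MS202 and was still present at 205MS203 entry would be tabulated as present at baseline, with no shift. The change-from-baseline half of each Table 8 vital-sign criterion would be affected in the same way.

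Long-term safety is the primary objective (Section 6.1.1), and change in laboratory values is a named secondary endpoint (Section 6.2.2). The subjects concerned came through the longest chain of preceding DAC HYP studies.

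**Working it through.** The plan states no figure to reproduce, and Section 16.6 says there is no formal sample size calculation. The check traces first exposure for each route of entry and then counts the subjects concerned.

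**Step 1. Where first exposure falls, by route**

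| Route into 205MS303 | First DAC HYP according to the study history | Covered by the Section 16.4.4 list? |
|---|---|---|
| 205MS301, Avonex arm | 205MS303 | Yes |
| 205MS301, DAC HYP arm | 205MS301 | Yes |
| 205MS203, from a DAC HYP arm of 205MS201 | 205MS201 | No; the list offers 205MS203 |
| 205MS203, from the placebo arm of 205MS201 | 205MS202 (inferred, not stated) | No; the list offers 205MS203 |

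The only route into 205MS203 that Section 5.1 describes is through completed 205MS202, as continued therapy. So 205MS203 is not the study of first receipt for these subjects. The list is closed in its wording, and it matches the definition of parent studies in Section 7.1, so 205MS201 and 205MS202 cannot be read into it. The laboratory examples concern 205MS301 only and do not correct it.

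**Step 2. Is this an artefact of mixing protocol versions?** No. The history in Section 5.1 is from the Version 2 text, because the introduction of the latest version is not shown. Version 2 has the same baseline rule and the same list in its own Section 16.4.4, so the conflict exists within one version and is carried into the latest text.

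**Step 3. How many subjects?** Inputs: about 1600 planned subjects, of whom about 400 are eligible from 205MS203 and 205MS302 together (Section 7.1, Version 2); 113 enrolled in 205MS302 (Section 5.1).

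- All 113 from 205MS302 roll over: 400 − 113 = 287; 287/400 = 71.8% of these entrants; 287/1600 = 17.9% of the study.
- None of the 113 roll over: 400; 400/1600 = 25.0%.

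**Step 4. Where the corrected baseline would lie.** With 1:1:1 allocation in 205MS201, two of the three arms received DAC HYP. Assuming equal retention across arms:

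- First exposed in 205MS201: 287 × 2/3 ≈ 191, or 400 × 2/3 ≈ 267.
- First exposed in 205MS202: 287 × 1/3 ≈ 96, or 400 × 1/3 ≈ 133.
- First exposed in 205MS203: none.

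The documents do not say how many subjects had abnormal values at 205MS203 entry. The direction of the effect is clear (fewer recorded shifts), but its size in the tables cannot be computed.

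**The case against.** The best defence is that the operative words are correct. First receipt, the baseline of DAC HYP treatment and the start of DAC HYP treatment each give a pre-drug value in 205MS201 or 205MS202 when read literally. The list sits in an explanatory sentence about where first receipt could fall, and it reuses the defined parent studies. This stands in part. A reader might infer that the plan firmly prescribes an on-drug baseline for these subjects; it does not. It contradicts itself, and the on-drug reading follows only if the list is given precedence. But nothing in the section says which statement governs, so the list still has to be corrected.

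A reader might also infer that some subjects would have no vital-sign baseline, because Section 14.1 says tests from the last 205MS301 visit, within 28 days of first dose, "may be used as baseline data for Study 205MS303", whereas the default rule asks for a value on the dosing day. The documents do not support this. The default yields to specific rules, and both laboratory values and vital-sign shifts have one. An accepted value from the last 205MS301 visit can serve as the baseline evaluation at the start of treatment. What remains is uneven wording between measures.

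A third inference would be that all 205MS203 entrants had one to two years of drug on board at that baseline. Section 5.1 says that 205MS202 gave up to 12 further months and included a washout in some previously treated subjects, and it does not say whether those subjects were back on drug at 205MS203 entry. For them, only previous exposure can be claimed.

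Finally, the consequence is limited. The analyses are largely descriptive. The worst post-baseline laboratory categories relative to the ULN, which may be presented, and the absolute limits in Table 8 do not depend on the baseline value. That is correct and bears on severity.

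**Conclusion.** The point holds as an internal contradiction. Section 16.4.4 defines the safety baseline by first exposure, then names a study that cannot be the place of first exposure for the 205MS203 route and omits the two that can. If the list is applied, laboratory shifts and vital-sign changes in those subjects are measured from a previously exposed value and are not comparable with those of 205MS301 entrants.

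The number concerned is about 287 (about 18% of 1600) if all 113 from 205MS302 enter, and up to about 400 (25%) if none do. Both figures assume that the planned 400 actually enter. The protocol gives 400 as an approximate number eligible, so 287 is a conditional figure and not a minimum. First dosing of former placebo subjects in 205MS202 is inferred from the study history.

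The primary endpoint, AE and SAE incidence, does not use this baseline. Severity: should-fix.

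**What to change.** Amend the list in Section 16.4.4 so that, for subjects entering through 205MS203, first receipt of DAC HYP is placed in 205MS201 or 205MS202, whichever applies to the subject. State that their baseline laboratory values and vital signs come from those studies' databases.

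For consistency, apply the existing laboratory rule to all safety measures: the last non-missing value before or on the day of the first-ever DAC HYP dose in any study. This also removes the uneven wording between the default rule and the laboratory and vital-sign rules.

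The cost is about two sentences of text, plus retrieval and merging of data from earlier studies in the programme, which the sponsor should already hold. No new assessments are needed. It is best done before the shift tables are programmed.
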